5.2.2 Patient Completed Efficacy Questionnaires

When these assessments are required at the times outlined in Table 1, they should be the first tasks done at any visit, and prior to study medication dosing.

The KSS is derived from the patient-administered DHAF (Appendix 2), and is the average on a 0 to 10 scale (0 = None, 10 = Very Severe) of 5 separate scales – rash, feeling of fever and chills, joint pain, eye redness and pain, and fatigue.

The DHAF is designed using a linear rating scale of circles in half-step units (e.g. 0.5, 1.0, 1.5, 2.0, etc.), which are marked 0 (none, no severity) to 10 (very severe)^{2.5}. Patients will select the circle on the scale that they determine most accurately represents severity of the symptom that they have experienced during the last 24 hours.

The DHAF will be completed daily by the patient. Daily KSS will be calculated by averaging the sum of the 5 individual symptom scores. KSS during a specified time period will further be calculated by averaging the sum of daily KSS scores during the time period.

Patients will be provided a quiet, private place to complete the assessments. Patients will be instructed to answer all the questions to the best of their ability and without help from others (study staff, family, or friends). The study staff should review the questionnaires after they are completed and encourage patients to complete any missing information. Patients can refrain from answering any question. Study staff will record the refusal of patients to answer any question in the source documents.

5.2.2.1 Re-emergence of CAPS Symptoms

Re-emergence of CAPS symptoms will be assessed after ATI-450 is discontinued following completion of the treatment period. Re-emergence is defined as an increase in daily KSS of ≥ 3 from baseline for at least two consecutive days.

5.2.3 High Sensitivity C-reactive Protein and Serum Amyloid A

Blood samples for evaluation of hsCRP and SAA will be collected at the times specified in Table 1. Samples will be shipped to a central laboratory. Specific instructions for collection, processing, storage and shipment of blood samples will be provided in a separate laboratory manual.

The normal range for serum hsCRP and SAA is defined as $\leq 10 \text{mg/L}$ for both.

5.3 Safety Assessments

5.3.1 Adverse Events

AEs will be followed, recorded, and reported in line with the procedures described in Section 7.

5.3.2 Clinical Laboratory Evaluations

Laboratory assessments during treatment will be performed by a central laboratory. Blood and urine samples will be collected at the times indicated in Table 1. On dosing day(s), sampling for the analysis of clinical laboratory parameters will be performed before the administration of study medication.

Unless indicated otherwise, all laboratory samples will be processed and shipped to the central laboratory, as described in the central laboratory manual. The central laboratory will analyze the samples or send them to reference laboratory(ies) for analysis, as indicated in the manual. Refer to the central laboratory manual for the maximum total volume of blood to be collected per patient throughout the study.

The following parameters will be assessed:

Hematology: hemoglobin, hematocrit, red blood cells, platelets, total WBC count, differential WBC count, and ANC

Coagulation: INR, partial thromboplastin time, and prothrombin time

Biochemistry: albumin, alkaline phosphatase (ALP), ALT, amylase, AST, blood urea nitrogen (BUN), calcium, creatine phosphokinase, hsCRP, creatinine, gamma glutamyltransferase, glucose, inorganic phosphatase, lactate dehydrogenase, lipase, magnesium, potassium, SAA, sodium, chloride, bicarbonate, total bilirubin, total protein, and uric acid

Lipids: total cholesterol, high-density lipoprotein, low-density lipoprotein, and triglycerides

Urinalysis: pH, specific gravity, creatinine, glucose, bilirubin, blood, and protein

Refer to the laboratory manual for details regarding the collection, processing, and shipping of the blood and urine samples.

The investigator must review the laboratory report, document this review, and record any clinically relevant changes occurring during the study in the AE section of the eCRF. If known, the underlying etiology of the clinically relevant laboratory changes should be reported as the AE, rather than the abnormal laboratory result itself. The laboratory reports must be filed with the source documents. Clinically significant abnormal laboratory findings are those that are not associated with the underlying disease under study, unless judged by the investigator to be more severe than expected for the patient's condition.

All laboratory tests with values considered clinically significantly abnormal during the patient's participation in the study or within 30 after the last dose of study medication should be repeated until the values return to normal, or baseline, or are no longer considered clinically significant by the investigator or medical monitor.

If such values do not return to normal/baseline within a period of time judged reasonable by the investigator, then the sponsor should be notified.

5.3.2.1 Potential Drug-induced Liver Injury

Hy's Law cases have the following 3 components:

- 1. The drug causes hepatocellular injury, generally shown by a higher incidence of \geq 3-fold elevations above the ULN of ALT or AST than the placebo
- 2. Among study patients showing such aminotransferase elevations, often with aminotransferases much greater than 3×ULN, one or more also shows elevation of serum total bilirubin to >2×ULN or INR >1.5, without initial findings of cholestasis (elevated ALP)
- 3. No other reason can be found to explain the combination of increased aminotransferase and total bilirubin, such as viral hepatitis A, B, or C; evidence for biliary obstruction; acute alcoholic hepatitis (recent drinking and AST >2×ALT are supportive); recent history of severe hypotension or congestive heart failure; other underlying viral disease; pre-existing or acute liver disease; or another drug (including non-prescription products such as herbal supplements) capable of causing the observed injury

During the study, the investigator will remain vigilant for increases in liver biochemistry. The investigator is responsible for determining whether a patient meets potential drug-induced liver injury criteria at any point during the study.

In the event that a patient shows laboratory results of:

- AST or ALT:
 - >5×ULN persisting for 2-weeks after study medication interruption or second occurrence of >5×ULN

- \circ >3×ULN and (total bilirubin >2×ULN or INR >1.5)
- >3×ULN with appearance of fatigue, nausea, vomiting, right upper quadrant pain or tenderness, fever, rash, and/or eosinophilia (>5%)

Please refer to Appendix 1 Possible Hy's Law Liver Chemistry Action and Follow-up Assessments Possible Hy's Law Liver Chemistry Action and Follow-up Assessments for further information.

5.3.3 Pregnancy

All patients are required to meet the requirements relating to pregnancy and use of contraception described in the inclusion and exclusion criteria (see Section 4.1 and Section 4.2, respectively).

Serum beta human chorionic gonadotrophin (β -hCG) testing will be performed for female patients of childbearing potential at screening (within 28 days of Day -1), and a urine pregnancy test will be performed on Day 1 (prior to dosing) and throughout the study.

The pregnancy test must be negative for the patient to be eligible. The serum pregnancy tests will be analyzed by the central laboratory, and the urine pregnancy tests will be analyzed locally.

Monitoring for pregnancies in female patients will continue from the patient's inclusion in the study until the follow-up visit. Male patients will be required to inform the investigator if their partner becomes pregnant during the study. The investigator should inform the sponsor within 24 hours of learning of the pregnancy or partner pregnancy by completing and submitting a pregnancy report form to the sponsor (or designee).

If a patient becomes pregnant, study medication will be permanently discontinued and she will be withdrawn from the study after completing the assessments planned for the end of study visit (see Table 1). Any pregnant patient and the fetus will be closely followed up throughout the duration of the pregnancy to determine the outcome (including spontaneous miscarriage, elective termination, normal birth, or congenital abnormality). The investigator will ask the patient to provide informed consent to record information on the health of the baby. Generally, follow-up will be required for no longer than 6 to 8 weeks beyond the estimated delivery date.

While pregnancy itself is not considered to be an AE or SAE, any pregnancy complication or elective termination of a pregnancy for medical reasons will be reported as an AE or SAE. Abnormal pregnancy outcomes (e.g., spontaneous abortion, fetal death, stillbirth, congenital abnormalities, ectopic pregnancy) will be considered SAEs.

For any male study patient whose partner becomes pregnant, the investigator will attempt to collect pregnancy information on the male patient's partner while the male patient is in this study.

The investigator will record pregnancy information on the appropriate form and submit it to the sponsor within 24 hours of learning of the partner's pregnancy. The investigator will obtain

informed consent from the female partner to collect information about the pregnancy and its outcome. Information on the status of the pregnant partner and the fetus will be forwarded to the sponsor. Generally, the follow-up will be no longer than 6 to 8 weeks following the estimated delivery date. Any termination of the pregnancy will be reported regardless of fetal status (presence or absence of anomalies) or indication for the procedure. Abnormal pregnancy outcomes (e.g., spontaneous abortion, fetal death, stillbirth, congenital abnormalities, ectopic pregnancy) will be considered SAEs.

5.3.4 12-lead Electrocardiogram

Triplicate 12-lead ECG will be recorded after the subject has been resting for at least 5 minutes in the supine position. as outlined in Table 1 using an ECG machine that automatically calculates the heart rate and measures PR, QRS, QT, and QTc intervals. The ECG tracing should clearly identify the patient, include the date and time of the assessment and the signature and date of the person who made the interpretation; the tracing will be archived at the study site. Abnormal, clinically significant ECG results will be recorded as AEs.

5.3.5 Vital Signs

Vital signs will be measured prior to dosing and immediately following dosing in a semi-supine position after 5 minutes' rest and will include temperature, systolic and diastolic blood pressure, pulse, and respiratory rate. Abnormal, clinically significant vital sign results will be recorded as AEs. If known, the underlying etiology for the abnormal clinically significant vital sign will be recorded as an AE rather than the vital sign itself.

5.3.6 Physical Examination

The complete physical examination will include assessments of the standard physical examination items, including general appearance, skin, eyes, ears, nose, throat, head and neck, heart, chest and lungs, abdomen, extremities, lymph nodes, musculoskeletal, neurological, and other body systems, if applicable, for describing the status of the patient's health.

The brief physical examination will include, at a minimum, signs of CAPS.

Body weight and height will also be measured and recorded. The patient should be dressed in lightweight clothing, without shoes.

Investigators should pay attention to clinical signs related to previous serious illnesses. Any new abnormalities or worsening of existing abnormalities should be reported as AEs, as appropriate (see Section 7).

5.4 Pharmacokinetics and Pharmacodynamics

Blood samples for PK and PD evaluation will be collected at the times specified in Table 1. Samples will be shipped to a central laboratory. Specific instructions for collection, processing, storage, and shipment of blood samples will be provided in a separate laboratory manual.

6 TREATMENTS

6.1 Investigational Product(s)

6.1.1 Description of Investigational Product(s)

Test Product

Substance: ATI-450
Strength: 50 mg
Mode of administration: Oral tablets

Manufacturer: Emerson Resources

6.1.2 Preparation, Handling, and Storage

The investigator (or designee) is responsible for the safe and proper storage of study medication at the site. ATI-450 and placebo will be stored under controlled conditions according to the storage requirements described on the label(s). Study medications should be stored at 15°C to 25°C (59°F to 77°F), away from heat moisture and direct light. The investigator (or designee) will instruct the patients to store the study medication in accordance to the instructions on the label(s).

6.1.3 Packaging, Labeling, and Shipment

ATI-450 will be packaged and labeled in accordance with all applicable regulatory requirements and Good Manufacturing Practice guidelines.

ATI-450 will be supplied in high-density polyethylene bottles.

Study medication will be shipped and stored under controlled conditions according to the storage requirements.

Refer to the pharmacy manual for full details for packaging, labeling, and shipment of the study medication.

6.2 Blinding

This is an open-label trial.

6.3 Dose and Administration

ATI-450 will be administered as oral tablets for a total of 100 mg daily. Doses will be administered twice daily (50 mg BID).

6.4 Precautions and/or Lifestyle Considerations

There are no lifestyle considerations (such as dietary or physical activity restrictions) for this study.

6.5 Prior Medication and Procedures

The following are considered exclusionary if taken within the defined period prior to the screening visit:

- 1. Systemic immunosuppressant or immunomodulatory therapy (e.g., etanercept, alefacept, infliximab, methotrexate) within 16 weeks prior to Visit 2 (excluding anti-IL-1 therapy for treatment of CAPS).
- 2. JAK inhibitors (systemic and topical) within 4 weeks prior to Visit 2.
- 3. Systemic corticosteroids within 4 weeks prior to Visit 2 (Intranasal, inhaled, and topical ocular corticosteroids are allowed).

6.6 Concomitant Medication

The following medications are prohibited during the duration of the study:

- 1. Systemic immunosuppressant or immunomodulatory therapy (excluding anti-IL-1 therapy for treatment of CAPS during screening and follow-up period). See section 3.1 for washout information.
- 2. JAK inhibitors (systemic and topical).
- 3. Systemic corticosteroids (Intranasal, inhaled, and topical ocular corticosteroids) are allowed.

All medication (including vaccines, over-the-counter or prescription medicines, vitamins, and/or herbal supplements) taken from 30 days before start of screening until the end of the follow-up period will be recorded in the appropriate section of the eCRF. The following details must be recorded in the eCRF:

- Medication name (ideally the generic name)
- Reason for use
- Start and end date of administration
- The dose and frequency of administration

The medical monitor should be contacted if there are any questions regarding prior or concomitant medication or procedures.

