4.2 Exclusion Criteria

A patient who meets any of the following exclusion criteria will not be eligible for inclusion in the study:

1. Participation in any clinical study with an investigative agent within 12 weeks prior to entry or within 5 half-lives of the investigational agent.

- 2. Being treated with another immuno-suppressive agent (i.e., in addition to an anti-IL-1 product) for CAPS syndrome (anti- IL1 therapy will have been used for at least 6 months and will be stopped at study entry).
- 3. Use of any of the following treatments within the indicated washout period prior to the baseline visit:
 - a. Systemic immunosuppressant or immunomodulatory therapy (e.g., etanercept, alefacept, infliximab, methotrexate) within 16 weeks prior to Visit 2 (excluding anti-IL-1 therapy for CAPS).
 - b. Janus Kinase (JAK) inhibitors (systemic and topical) within 4 weeks prior to Visit 2.
 - c. Systemic corticosteroids within 4 weeks prior to Visit 2. (Intranasal, inhaled, and topical ocular corticosteroids are allowed).
- 4. History of being immunocompromised, including a positive HIV test result at screening.
- 5. A positive Hepatitis B surface antigen (HBsAg) or Hepatitis C antibody test result is not allowed.
- 6. Live vaccination within 3 months prior to the start of the trial, or during the trial.
- 7. History of recurrent and/or evidence of active bacterial, fungal, or viral infections.
- 8. History or evidence of active or latent tuberculosis (TB).
- 9. Tests performed at a central laboratory at screening that meet any of the criteria below (out of range labs may be rechecked one time, after consultation with sponsor or designee, before patient is considered a screen failure):
 - White blood cell (WBC) count $< 3.0 \times 10^3$ cells/mm³
 - Absolute neutrophil count (ANC) <1.5×10³ cells/mm³
 - Lymphocyte count <0.5×10³ cells/mm³
 - Platelet count <100×10³ cells/mm³
 - Hemoglobin <10 g/dL
 - Aspartate aminotransferase (AST) or alanine aminotransferase (ALT) ≥1.5×upper limit of normal (ULN)
 - Total bilirubin level $\ge 2 \times ULN$ unless the patient has been diagnosed with Gilberts' disease and this is clearly documented
 - Estimated glomerular filtration rate (eGFR), <40 mL/min/1.73m² based on Modification of Diet and Renal Disease formula
- 10. Any clinically significant laboratory abnormality that would affect interpretation of study data or safety of the patient's participation in the study, per judgment of investigator.

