5.2.1.2 Time to Relapse

Time to relapse will be assessed during the treatment period. Relapse is defined as a two-point worsening on the PGA scale.

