8.2 Analysis Populations

- The ITT population will include all patients who have been administered at least one dose of study medication.
- The PP population will include all patients who complete 12-weeks of treatment and 4-weeks of follow up and have completed assessments.

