8.4 Statistical Methods

8.4.1 Efficacy Analyses

All efficacy summaries will be conducted on both the ITT and PP populations.

- Proportion of participants in disease remission over time; where disease remission is defined as having a PGA score of minimal or better and a hsCRP and SAA value within the normal range or within 30 percent of the baseline value (ITT and PP population).
- Proportion of participants in clinical remission over time; where clinical remission is defined as having a PGA score of minimal or better (ITT and PP population).
- Time to relapse; where relapse is defined as a two-point worsening on the PGA scale in the ITT population.

- Proportion of participants who experience a daily increase in KSS \geq 3 on at least two consecutive days after discontinuation of ATI-450 over time (PP population).
- Proportion of participants who maintain a mean KSS of no more than 2 higher than baseline for at least 6 out of 8 weeks in the ITT and PP population.
- Change from baseline in PGA and KSS scores will be reported descriptively over time (ITT and PP population).
- Change from baseline in hsCRP and SAA and percent change from baseline in hsCRP and SAA will be summarized over time using continuous statistical summary measures. Determination of sustained treatment effect for hsCRP and SAA will be based upon the median percent change from baseline in the ITT and PP population.

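### Section 6.6 lists systemic corticosteroids under prohibited medication yet says they are allowed, and no analysis rule in the protocol covers efficacy data after their use

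*Combined protocol and SAP*

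**What the plan says.** Section 6.6 (Concomitant Medication) introduces a numbered list with "The following medications are prohibited during the duration of the study". Item 1 covers systemic immunosuppressants and immunomodulators in general, item 2 covers JAK inhibitors, and item 3 is "Systemic corticosteroids (Intranasal, inhaled, and topical ocular corticosteroids) are allowed".

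The pre-baseline rules are worded differently. Section 6.5 has "Systemic corticosteroids within 4 weeks prior to Visit 2 (Intranasal, inhaled, and topical ocular corticosteroids are allowed", with the closing bracket after the last word. Exclusion criterion 3c in section 4.2 has "Systemic corticosteroids within 4 weeks prior to Visit 2. (Intranasal, inhaled, and topical ocular corticosteroids are allowed", closed in the same place, and criterion 3c in the synopsis follows the same pattern.

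On the efficacy side, section 5.2.1.2 states "Relapse is defined as a two-point worsening on the PGA scale", and section 8.4.1 lists "Time to relapse; where relapse is defined as a two-point worsening on the PGA scale in the ITT population". Clinical remission is a PGA of absent or minimal; disease remission adds conditions on hsCRP and SAA (5.2.1.1). Section 8.2 defines the per-protocol set by completion: "The PP population will include all patients who complete 12-weeks of treatment and 4-weeks of follow up and have completed assessments". Section 6.6 also requires that all medication taken "will be recorded in the appropriate section of the eCRF".

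**The concern.** An entry in a list of prohibited drugs that ends by allowing the drug gives a site no single instruction. One site could treat a systemic steroid course during the 12 weeks as a deviation, and another could treat it as permitted. Two other parts of the protocol depend on which it is: noncompliance as a reason to stop study drug (4.4.1) and the classification of important deviations (11.2).

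The statistical consequence is limited to efficacy. The trial is open-label and single-arm, with up to 10 patients, so no control group shows what a concomitant treatment contributes. If systemic steroids improve the measures from which remission, relapse and KSS are derived, data collected after their use would be credited to ATI-450. Nothing in the definitions would flag this.

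**Working it through.** The plan gives no figure to reproduce: the sample size rests on feasibility (8.3). The check is a comparison of texts plus one line of arithmetic.

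**1. Where the bracket closes**

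| Place | Period governed | What the permission attaches to, as printed |
|---|---|---|
| Synopsis, exclusion 3c | 4 weeks before Visit 2 | nasal, inhaled and ocular products only |
| 4.2, exclusion 3c | 4 weeks before Visit 2 | nasal, inhaled and ocular products only |
| 6.5, item 3 | 4 weeks before Visit 2 | nasal, inhaled and ocular products only |
| 6.6, item 3 | whole study | systemic corticosteroids, with the local routes as examples |

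Only 6.6 has the bracket closing before the verb. Read literally, it also makes local routes examples of systemic treatment, which is not coherent. Both facts point to a punctuation slip. The summary of changes does not mention the item, so this is current text.

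**2. Whether another section settles on-treatment use.** The three parallel items stop at Visit 2. Item 1 of 6.6 prohibits systemic immunosuppressants in general terms. A site could apply it to steroids, but the list handles steroids as a separate item. The stopping list in 4.4.1 does not name them. No section other than 6.6 names systemic corticosteroids during treatment.

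**3. Whether an analysis rule catches such use**

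- Remission and relapse (5.2.1, 8.4.1): no reference to concomitant medication.
- KSS endpoints (5.2.2, 8.4.1): no reference either.
- Per-protocol set (8.2): completion only, so a completer who took steroids stays in both the ITT and PP sets.
- Missing data (8.4.5): addresses absent values, not values observed after another treatment.

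**4. Size.** Let n be the number analysed and k the number counted in remission, including one patient whose status depends on steroid use.

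- Reclassifying that patient: k/n − (k − 1)/n = 1/n. With n = 10 this is 1/10 = 10 percentage points, and it is larger if fewer enrol.
- Leaving that patient's visit out instead: k/10 − (k − 1)/9 = (10 − k)/90. This runs from 9/90 = 10 points at k = 1 to 0 at k = 10.

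A summary without the exposed visits can therefore move by less than 10 points, so it should also state how many patients were exposed.

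**The case against.** The best case against the point is that this is a typing error with safeguards around it. The heading and three parallel items point the same way, so a careful site would probably see what happened. Item 1 may cover systemic steroids anyway. Section 6.6 sends questions on concomitant medication to the medical monitor and requires the name, reason, dates, dose and frequency of every medication. Important deviations are discussed with the medical monitor (11.2). With up to 10 patients, exposed cases could be reviewed one by one. The primary endpoint is safety; efficacy is exploratory in the synopsis and secondary in Table 2. Section 8.1 leaves statistical detail to a separate SAP, whose text is not among the documents supplied.

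Most of this stands, and it lowers the weight of the point. It does not remove the contradiction from an operative rule. Recording use identifies exposed patients but does not fix in advance how their data are summarised, and in an open-label trial that choice is better made before the data are seen. As to the SAP, the finding is only that the protocol contains no such rule.

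A reader might infer that the protocol deliberately permits systemic steroids during treatment, or that relapse will be masked by them. The documents support neither. The parallel items argue against an intended permission. The effect of steroids on the outcome measures is not stated anywhere, and expected use is not given. A reader might also conclude that every visit after any steroid use must be scored as not in remission. That is a debatable choice: without a time limit, a short course for an unrelated illness would count as failure for the rest of the study.

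**Conclusion.** The point holds as an internal contradiction with a modest gap in the analysis plan. Item 3 of 6.6 conflicts with its heading, probably through a misplaced bracket, and no other section resolves on-treatment use by name. The efficacy definitions and the per-protocol set would count data after such use without distinction.

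The size is up to 10 percentage points on a remission proportion per affected patient when 10 are analysed. This rests on two assumptions that the documents do not supply: that at least one patient takes a systemic steroid during treatment, and that doing so changes PGA, KSS, hsCRP or SAA enough to alter the patient's classification. The primary safety objective is not where this concern lies. The correction is worth making because it is specific and nearly free.

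**What to change.** 1. Reconcile item 3 of 6.6 with its own heading and with 4.2 and 6.5, so that only one reading remains. Which clinical rule applies is for the sponsor to decide.
2. Add to 8.4.1 or the SAP that remission, relapse and KSS summaries are shown with and without visits (for KSS, diary days) after on-treatment systemic corticosteroid use, with the number of exposed patients. Say whether data left out in this way are treated as missing under the multiple imputation in 8.4.5 or simply omitted.
3. Identify exposure from the eCRF medication records. The details that 6.6 requires do not name the route of administration. Either add it, or state that systemic use is judged from drug name, dose and reason.

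The cost is a corrected sentence in 6.6, a sentence or two in the analysis section, and one extra descriptive summary. If no patient is exposed, the two versions are identical and a line saying so is enough.
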